Supporting evidence for the safety and efficacy of this product in patients 2 years and older represents a major advancement in the treatment of AD given the challenges of managing this common, chronic dermatologic condition and the limitations of currently available therapies. All primary and secondary efficacy endpoints were statistically significant in the two previous Phase 3 vehicle-controlled studies, AN2728-AD-301 and AN2728-AD-302. Across the development program, crisaborole demonstrated an acceptable safety profile; the majority of adverse events (AEs) were mild and deemed unlikely or not related to investigational product, with no crisaborole treatment related serious adverse events (SAEs) (except 1 case of drug eruption in a Phase 2 study which was classified as possibly related).

This 4-week, randomized, assessor blinded, crisaborole ointment, 2%, vehicle and active (topical corticosteroid [TCS] and topical calcineurin inhibitor [TCI]) controlled study will determine the efficacy and safety of crisaborole ointment, 2% applied twice daily (BID) compared with vehicle in subjects ages 2 years and older with mild to moderate AD. The study will also evaluate the efficacy and safety of crisaborole ointment, 2% compared with the active controls; hydrocortisone butyrate cream, 0.1% [TCS] and pimecrolimus cream, 1% [TCI]. Hence, this study will, provide contextualization of the efficacy and safety of crisaborole ointment, 2% in the treatment of mild to moderate AD.

The crisaborole dose strength and regimen selected for this study has been demonstrated to be safe, well-tolerated and efficacious in subjects and healthy volunteers 2 years of age and older who participated in previous studies.

Hydrocortisone butyrate cream, 0.1% and pimecrolimus cream, 1% are approved products for the treatment of mild to moderate atopic dermatitis in subjects ages 2 years and older, and will be used as per their national approved label in this study.

Objectives and Endpoints:

Primary Efficacy Objective	Primary Efficacy Endpoint

To compare the efficacy of crisaborole ointment, 2% applied BID versus vehicle in pediatric and adult subjects, aged 2 years and older, with mild to moderate AD.	
Percent change from Baseline in the Eczema Area and Severity Index (EASI) total score at Day 29.
Primary Safety Objectives	Primary Safety Endpoints

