1.4. Rationale

1.4.1. Study and Dose Rationale

This 4-week, randomized, assessor blinded, vehicle and active (TCS and TCI) controlled study will determine the efficacy of crisaborole ointment, 2% applied BID compared with vehicle and evaluate the efficacy of crisaborole ointment, 2% applied BID compared with a TCS or TCI, in subjects ages 2 years and older with mild to moderate AD. The study will also evaluate the efficacy and safety of crisaborole ointment, 2% compared with the active controls; hydrocortisone butyrate cream, 0.1% [TCS] and pimecrolimus cream, 1% [TCI]. Hence, this study will, provide contextualization of the efficacy and safety of crisaborole ointment, 2% in the treatment of mild to moderate AD.

In the current treatment paradigm of mild to moderate AD there are only two main topical treatment options – TCS and the TCI pimecrolimus cream 1% (Elidel[®]). To fully inform the position of crisaborole ointment, 2% in relation to the available topical treatments for mild to moderate AD, both the TCS hydrocortisone butyrate cream 0.1% (a standard of care treatment) and pimecrolimus cream, 1% (a second line treatment) have been included as active comparators. The study will therefore provide contextualization of the efficacy of crisaborole ointment, 2% in the treatment of mild to moderate AD compared with hydrocortisone butyrate cream, 0.1% and pimecrolimus cream, 1%.

The dose strength and regimen of crisaborole for this study has been shown to be safe, well-tolerated and efficacious in subjects and healthy volunteers 2 years of age and older who participated in previously conducted studies. Crisaborole ointment, 2% applied BID was studied in two Phase 3, randomized, double-blind, vehicle-controlled studies, and a Phase 3 open-label long-term safety study. Data from the two controlled studies showed a statistically significant therapeutic effect compared to vehicle with no safety concerns in subjects 2 years and older. In the subsequent Phase 3 open-label extension study, crisaborole ointment, 2% applied BID, demonstrated that long-term use was well-tolerated and not associated with any systemic safety signals.

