4.1. Inclusion Criteria

4.1.1. Inclusion Criteria – All Cohorts

Subjects must meet all of the following inclusion criteria to be eligible for enrollment into the study:

1. Is male or female 2 years and older at the Screening visit/time of informed consent/assent.
2. Has a clinical diagnosis of AD according to the criteria of Hanifin and Rajka (See [Appendix 2](#)).
3. Has AD involvement of $\geq 5\%$ Treatable %BSA (excluding the scalp) at Baseline/Day 1.
4. Has an ISGA score of Mild (2) or Moderate (3) (excluding the scalp) at Baseline/Day 1.
5. Female subjects of childbearing potential who have a negative urine pregnancy test at the screening visit and negative urine pregnancy test at the baseline visit prior to randomization. A female is of childbearing potential if, in the opinion of the investigator, she is biologically capable of having children (includes any female who has experienced menarche and does not meet the criteria for females not of childbearing potential).
6. Female subjects of non-childbearing potential must meet at least 1 of the following criteria:
 - a. Achieved postmenopausal status, defined as follows: cessation of regular menses for at least 12 consecutive months with no alternative pathological or physiological cause; have a serum follicle-stimulating hormone (FSH) level confirming the postmenopausal state;
 - b. Have undergone a documented hysterectomy and/or bilateral oophorectomy;
 - c. Have medically confirmed ovarian failure.

All other female subjects (including female subjects with tubal ligations) are considered to be of childbearing potential.

7. Evidence of a personally signed and dated informed consent/assent document indicating that the subject [or parent(s)/legal guardian] has been informed of all pertinent aspects of the study.
8. Willing and able to comply with scheduled visits, treatment plan, laboratory tests and other study procedures.

4.1.2. Inclusion Criteria – Cohort 1

1. Subjects considered to be a candidate for hydrocortisone butyrate cream, 0.1% therapy according to the national approved labeling.

4.1.3. Inclusion Criteria – Cohort 2

1. Subjects who are not considered candidates for treatment with a topical corticosteroid because it is either inadvisable or not appropriate according to the national approved labeling. This may include:
 - Intolerance to topical corticosteroids;
 - Lack of effect of topical corticosteroids;

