4.3. Randomization Criteria

Subjects will be randomized into the study provided that the subject or caregiver [parent/legal guardian/legally acceptable representative] has signed an informed consent (or assent, if applicable) document to participate in the study, and the subject has undergone all screening procedures, and satisfies all inclusion and exclusion criteria for participation in the study at the Baseline visit. A centralized computer-generated randomization schedule will be used to assign subjects to the treatment groups.

Subjects will be assigned to one of two cohorts prior to randomization. Subjects will be enrolled into Cohort 1 if eligible to receive TCS therapy; randomization will be 1:1:2 to crisaborole ointment, 2%, the matching vehicle ointment for crisaborole, or hydrocortisone butyrate cream, 0.1%, respectively. Subjects will be enrolled into Cohort 2 if ineligible to receive TCS therapy and eligible to receive pimecrolimus cream, 1%; randomization will be 1:1:2 to crisaborole ointment, 2%, the matching vehicle ointment for crisaborole, or pimecrolimus cream, 1%, respectively.

Subjects will be assigned a subject identification number in the order of their screening for the study. The identifying number will be retained throughout the study.

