9.1. Sample Size Determination

A total of approximately 600 subjects will be enrolled into this study. Approximately 300 subjects who are eligible to receive TCS therapy (Cohort 1) will be randomized to crisaborole ointment, 2%, the matching vehicle ointment for crisaborole, or TCS with a

randomization ratio of 1:1:2. Approximately 300 subjects who are ineligible to receive TCS therapy and eligible to receive TCI therapy (Cohort 2) will be randomized to crisaborole ointment, 2%, the matching vehicle ointment for crisaborole, or pimecrolimus cream 1% with randomization ratio 1:1:2.

A sample size of 150 subjects in the crisaborole group combined from Cohort 1 and Cohort 2 and 150 subjects in vehicle group combined from Cohort 1 and Cohort 2 will provide 86% power to detect a 12% difference of EASI percent reduction from baseline at Day 29 between crisaborole and vehicle at the 0.05 (2-sided) significance level, assuming the common standard deviation of EASI percent reduction from baseline at Day 29 is 34%.

EASI was not collected in previous crisaborole studies. The 12% treatment effect in EASI percent improvement was converted from the ISGA response in the Phase 3 studies using a linear regression equation that evaluated the relationship between ISGA response rate and EASI percentage improvement from historical trial data of other topical products. From the crisaborole Phase 3 pooled data, the ISGA response rate is 32.1 % for crisaborole ointment, 2%, and 21.8% for vehicle. The converted EASI percent improvement is 38.9% and 26.8% respectively. The difference of EASI percent improvement between crisaborole ointment, 2% and vehicle is approximately 12%.

With sample size of 75 subjects in the crisaborole group and 150 subjects in the TCS or TCI groups, the half width of the 95% confidence interval for the difference of EASI percent reduction from baseline at Day 29 between crisaborole and active comparator is 9.4%. The sample size within each Cohort will also provide sufficient precision to enable contextualization of the efficacy of crisaborole in treating subjects with mild to moderate AD relative to each active comparator.

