5.1. Hypotheses and Decision Rules

This study was terminated. The termination decision was made for business reasons only and was not related to any safety or efficacy concerns regarding crisaborole. Only 40% of planned participants were enrolled at termination. Due to small sample size, no hypotheses testing and decision rules. No statistical analysis and comparison will be performed. Only descriptive summary will be generated for safety data and some efficacy endpoints.

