5.2. General Methods

In general, number and percent will be presented for binary and categorical variables. Number, mean, standard deviation, standard error of the mean, median, minimum, and maximum will be presented for continuous variables. In addition, graphics may be used to present the data – specific details will be outlined in the study List of Table (LOT).

Descriptive statistics will be provided for:

- Crisaborole ointment, 2% applied BID (Cohort 1);
- Crisaborole ointment, 2% applied BID (Cohort 2);
- Crisaborole ointment, 2% applied BID (combined Cohorts 1 and 2);
- Vehicle (combined Cohorts 1 and 2);
- Hydrocortisone butyrate cream, 0.1% BID (TCS, Cohort 1);
- Pimecrolimus cream, 1% BID (TCI, Cohort 2);
- Total – only for disposition, evaluation, demographic and baseline characteristics.

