6.6. Safety Summaries and Analyses

Safety analysis will be based on the SAF.

Safety data will be presented in tabular and/or graphical format and summarized descriptively, where appropriate. All safety endpoints will be listed and summarized in accordance with Pfizer Standards. Categorical outcomes (eg, AEs) will be summarized by subject counts and percentage. Continuous outcome (eg, blood pressure, pulse rate, etc) will be summarized using N, mean, median, standard deviation, etc. Change from baseline in laboratory data, and vital signs will also be summarized. Subject listings will be produced for these safety endpoints accordingly. Cohort 1 and cohort 2 will be combined for crisaborole and vehicle arms for all safety summaries and analyses.

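### Safety tables show crisaborole and vehicle only pooled over cohorts, so TCS and TCI cannot be read beside the subjects randomised with them

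*SAP*

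**What the plan says.** On safety, SAP 6.6 is explicit: "Cohort 1 and cohort 2 will be combined for crisaborole and vehicle arms for all safety summaries and analyses". The wording covers every safety table. The only summary by cohort among the subset analyses, in SAP 6.4, is for EASI.

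The general list of reporting groups in SAP 5.2 is different. It has crisaborole three times (Cohort 1, Cohort 2 and combined), vehicle once (combined only), TCS for Cohort 1 and TCI for Cohort 2. SAP 6 refers to that list for the efficacy and patient-reported summaries; 6.6 sets its own rule for safety.

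On design, Protocol 4.3 says "Subjects will be assigned to one of two cohorts prior to randomization", with 1:1:2 allocation inside each cohort. The third arm is hydrocortisone butyrate in Cohort 1 and pimecrolimus in Cohort 2. Protocol 4.1.3 describes Cohort 2 as subjects for whom a topical corticosteroid is unsuitable. Its examples are "Intolerance to topical corticosteroids", lack of effect, and disease on body regions where a TCS may be inappropriate.

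On purpose, the protocol summary and Protocol 1.4.1 both say: "The study will also evaluate the efficacy and safety of crisaborole ointment, 2% compared with the active controls". Protocol 1.4.1 adds that "this study will, provide contextualization of the efficacy and safety of crisaborole ointment, 2% in the treatment of mild to moderate AD".

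**The concern.** The TCS and TCI columns will stand beside a crisaborole column that mixes two populations. A subject in Cohort 2 could never have been allocated to TCS, and a subject in Cohort 1 could never have been allocated to TCI. Part of the crisaborole column is therefore not a concurrent randomised control for the active arm next to it. The same is true of the vehicle column.

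The cohorts differ by selection on corticosteroid history and body region. It is a reasonable inference, though not a documented fact, that this could affect local reactions. These are the events most likely to be read across: Protocol 1.4.2 gives application site pain as the one treatment-related event with a clinically relevant excess over vehicle, and lists application site reactions among the common effects of both active controls. A difference in case mix could then look like a difference between drugs, in either direction. SAP 5.1 plans no tests or comparisons, so the side-by-side columns are all the reader has.

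**Working it through.** **1. Plan's own figures.** Protocol 9.1 gives the cohort sizes: "With sample size of 75 subjects in the crisaborole group and 150 subjects in the TCS or TCI groups". With SD 34, the 95% half-width is 1.96 × 34 × √(1/75 + 1/150) = 9.42, which matches the stated 9.4%. The crisaborole-versus-vehicle power with 150 per arm and a difference of 12 reproduces as 86.4%, against the stated 86%. For efficacy, then, the comparison with each active control was sized within cohort, on 75 crisaborole subjects and not 150. The safety point itself rests on no stated figure.

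**2. Composition of the pooled column as planned.** Each cohort has about 300 subjects at 1:1:2, so 75 crisaborole, 75 vehicle and 150 active. Pooled crisaborole is 75 + 75 = 150, and so is pooled vehicle. The share from the cohort without the active arm in question is s = 75/150 = 50%.

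**3. Effect on a displayed rate.** Pooled rate = (1 − s) × own-cohort rate + s × other-cohort rate. Hence pooled − own = s × (other − own). At s = 0.5 the displayed rate is off by half the true difference between cohorts.

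**4. At termination.** SAP 5.1: "Only 40% of planned participants were enrolled at termination". That is 0.40 × 600 = 240 subjects. The split between cohorts is not given, so these are assumptions:

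| Split of 240 (Cohort 1 : Cohort 2) | Crisaborole : vehicle : active, Cohort 1 | Same, Cohort 2 | Pooled crisaborole | Non-matching share for TCS | Non-matching share for TCI |
|---|---|---|---|---|---|
| 50:50 | 30:30:60 | 30:30:60 | 60 | 50% | 50% |
| 30:70 | 18:18:36 | 42:42:84 | 60 | 42/60 = 70% | 18/60 = 30% |
| 70:30 | 42:42:84 | 18:18:36 | 60 | 30% | 70% |

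**5. Illustration with assumed rates.** Take a local reaction at 4.4% on crisaborole in Cohort 1 (the application site pain rate from the earlier studies, Protocol 1.4.2) and vary Cohort 2. The last column lets the Cohort 2 share run from 30% to 70%.

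| Assumed Cohort 2 rate | Pooled rate, s = 0.5 | Shift in contrast with TCS | Shift in contrast with TCI | TCS shift, 30–70% from Cohort 2 |
|---|---|---|---|---|
| 4.4% | 4.4% | 0 | 0 | 0 |
| 8.8% | 6.6% | +2.2 points | −2.2 points | 1.3 to 3.1 points |
| 13.2% | 8.8% | +4.4 points | −4.4 points | 2.6 to 6.2 points |

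For scale, the earlier crisaborole–vehicle difference in application site pain was 4.4 − 1.2 = 3.2 points.

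**6. Why crisaborole versus vehicle is unaffected.** Both arms have the same allocation share in each cohort, so both pooled columns have the same expected cohort mix.

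**7. Precision given up by reading within cohort.** Approximate 95% half-width at a common rate of 4.4%, from 1.96 × √(0.044 × 0.956 × (1/n₁ + 1/n₂)): as planned, 5.7 points (75 versus 150) against 4.6 points (150 versus 150). At 240 subjects split equally, it is 9.0 points (30 versus 60) against 7.3 points (60 versus 60).

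**The case against.** The strongest objection is that no formal objective asks for this. In Protocol 2 and SAP Table 2, crisaborole safety is set against vehicle, and TCS and TCI safety is stated with no comparator. The secondary objectives against the active controls cover efficacy and reported outcomes only. The within-cohort rule in Protocol 3 and 9.2.1 sits with efficacy, and Protocol 9.3 sets no cohort rule for safety. All of this stands, and it is why the point is a presentation gap and not a breach. It does not remove the announced evaluation. TCS and TCI safety is also a primary objective, so those columns will be printed beside crisaborole and will be compared.

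Second, SAP 5.1 disclaims any comparison after early termination. That is true of tests and intervals, but a table with adjacent columns is still read across.

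Third, the by-cohort columns will be sparse. With 30 per arm, one event is 3.3 points; with 18, it is 5.6. At 4.4% and 1.2%, about 1.3 and 0.4 events are expected per 30. This stands as a limit on interpretation. It is a reason to show both views and not to show only the pooled one, whose gain in precision is modest (7.3 against 9.0 points).

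Fourth, the case-mix effect is plausible but not shown, and the 30:70 to 70:30 range is an assumption. Both are correct. The by-cohort columns are what would show whether the cohorts differ.

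Fifth, vehicle by cohort is not in SAP 5.2, and subject listings are planned. Vehicle by cohort goes beyond 5.2, but it completes each randomised set at trivial cost. Listings might allow someone to rebuild the view, but they are not a summary.

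**Conclusion.** The concern holds. As written, SAP 6.6 leaves no planned safety summary in which TCS or TCI stands beside only the crisaborole and vehicle subjects randomised with it, although the protocol twice announces a safety evaluation against those controls. As planned, half of each pooled column is non-matching. At about 240 subjects the share is unknown, and would be 30% to 70% if the cohort split lay between 30:70 and 70:30 (assumption). The distortion in any event rate is that share times the true difference between cohorts, which the documents do not allow one to estimate; it is zero if the cohorts have equal rates. The crisaborole-versus-vehicle safety reading is not affected. SAP 5.2 and 6.6 also need to be aligned, because 5.2 lists crisaborole by cohort and 6.6 removes that split for safety. The change is worth making, and nothing here amounts to a departure from the protocol.

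**What to change.** In SAP 6.6, keep the pooled crisaborole and vehicle columns for the crisaborole-versus-vehicle objective. Add crisaborole and vehicle by cohort to the key safety tables: treatment-emergent AEs, SAEs, local tolerability AEs, and withdrawals due to AEs. Set TCS beside the Cohort 1 columns and TCI beside the Cohort 2 columns. Amend 5.2 so that its list of groups agrees with 6.6, including vehicle by cohort. Keep everything descriptive, and add a footnote that the by-cohort counts are small and that the pooled columns are not the randomised comparator for TCS or TCI.

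The cost is four extra columns in a few tables and no new data; the by-cohort crisaborole groups are already defined in 5.2. The drawback is thin cells: about 30 crisaborole and 30 vehicle per cohort under an equal split of 240, or 18 to 42 per arm under a 30:70 to 70:30 split (both assumptions).

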6.6.1. Adverse Events

The safety data will be summarized in accordance with Pfizer Data Standards. All safety data will be summarized descriptively through appropriate data tabulations, descriptive statistics, categorical summaries, and graphical presentations. Safety endpoints for the study include:

- Treatment-emergent AEs and SAEs;
- Local tolerability AEs/SAEs;
- Withdrawals from treatment/study due to AEs.

6.6.2. Laboratory Data

Laboratory data will be listed and summarized in accordance with the Pfizer reporting standards.

6.6.3. Vital Signs

Vital signs will be summarized at baseline, Day 29/End of treatment/Early termination visits.

6.6.4. Physical Examination

Physical examinations will be summarized at baseline, Day 29/End of treatment/Early termination visits.

7. INTERIM ANALYSES

7.1. Data Monitoring Committee

This study uses an external data monitoring committee (E-DMC).

The E-DMC will be responsible for ongoing monitoring of the safety of subjects in the study according to the charter. The recommendations made by the E-DMC to alter the conduct of the study will be forwarded to Pfizer for a final decision. Pfizer will forward such decisions, which may include summaries of aggregate analyses of endpoint events and of safety data that are not endpoints, to regulatory authorities, as appropriate.

7.2. Interim Analyses and Summaries

There is no plan for an interim analysis.

8. REFERENCES

None.

9. APPENDICES

Appendix 1. Definition and Use of Visit Windows in Reporting

Visit windows will be used for efficacy variables, and for any safety data that display/summarize by study visit.

Visit Label	Target Day	Definition [Day window]
Screening		Days -35 to Day -1
Baseline	Day 1, Baseline	Day 1*
Day 8	8	Days 2 to 11
Day 15	15	Days 12 to 18
Day 22	22	Days 19 to 25
Day 29/ End of Treatment/ Early Termination	29	Days 26 to last dose +7
Day 43	43	Last dose +8 to end of study

* The baseline of Peak pruritus NRS/scale and **CCI** is the average of 7-day scores immediately prior to Day 1 (Day -6 to Day 1)

For the lab values, if the calculated study Day for the labelled baseline visit is not study Day 1 but falls within 28 days before the start of the study dosing, then that data should be used for the baseline instead of leaving baseline missing.

For the other values, if the calculated study day for the labelled baseline visit is not study Day 1, but falls before the start of the study dosing, then that data should be used for the baseline instead of leaving baseline missing.

If two or more visits fall into the same window, keep the one closest to the Target Day. If two visits are equaled distant from the Target Day in absolute value, the later visit should be used.

Safety analysis may follow Pfizer standards.

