4. SUBJECT ELIGIBILITY CRITERIA

This study can fulfill its objectives only if appropriate subjects are enrolled. The following eligibility criteria are designed to select subjects for whom participation in the study is considered appropriate. All relevant medical and nonmedical conditions should be taken into consideration when deciding whether a particular subject is suitable for this protocol.

Subject eligibility should be reviewed and documented by an appropriate member of the investigator's study team before subjects are included in the study.

Subjects screening for the study prior to informed consent approval by IRB/EC for amendment 3 should complete the version of the study for which they consented. Subjects screening for the study after IRB/EC approval of the amendment 3 version of the protocol and consent should complete the amendment 3 version of the study.

Subject eligibility for the sub-study will be reviewed and documented according to additional criteria specified in Appendix 4. The sub-study informed consent process will be separate and in addition to the informed consent process for the main study.

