3. The **tape-strips lesional target skin site** will preferably be adjacent to the AD lesional target skin site and will have a local ISGA score of 2 or 3. If there are not two adjacent target skin sites for OCT and tape-strips, an alternate location for tape-strips may be located at the site bilateral to the OCT target skin site. The same target skin site will be used for all tape-strip collections throughout the duration of the sub-study. This target skin site will be recorded on a sub-study body map for reference so that the location is used consistently for all subsequent collections. This area should be ≥ 3 cm in each diameter without overlapping with the AD lesional target skin site.

Treatment of target skin sites

The OCT AD lesional target skin site and the tape-strips AD lesional target skin site will be included in the main study treatment area and will be treated for 28 days with investigational product even if the AD resolves during the course of treatment.

The non-lesional target skin site at the volar forearm will be free of AD, however this area will be treated with investigational product for the duration of the 28-day treatment period.

Treatment with investigational product on all target skin sites should be withheld on all study visit days until after the study visit procedures. The time since last investigational product treatment of the target skin sites and the time of study visit procedures will be collected.

Local ISGA score

A local target ISGA score will be obtained and recorded for all three target skin sites on Baseline/Day 1, Day 8, Day 15, Day 22, Day 29, and Day 60 in addition to the overall ISGA.

EASI assessment

An EASI assessment will be performed on Day 60 in addition to the Days specified in the main protocol (Baseline/Day 1, Day 8, Day 15, Day 22, Day 29 and Day 43).

Photography of target skin sites

Each sub-study target skin site will be photographed in addition to any photography performed for the main study at Baseline/Day 1, Day 15, and Day 29. Each photograph will be labeled with the corresponding target skin site.

OCT measurements, TEWL, and Tape-strips

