1. VERSION HISTORY

This SAP for Study C3291037 is based on the protocol amendment 3 dated 12AUG2019.

Table 1. Summary of Major Changes in SAP Amendments

Version/Date	Associated Protocol Amendment	Specific Changes	Rationale
1 16MAY2018	Original 16MAR2018	Not Applicable	Not Applicable
2 27SEP2019	Protocol Amendment 3 12 Aug 2019	Removal of telephone follow-up at Day 36; addition of a clinic visit at Day 43; addition of restrictions to concurrent medications during the follow-up phase; and changes to the pruritis scale descriptions, endpoints, and analysis.	Per Protocol Amendment 3
3 10NOV2020	Protocol Amendment 3 12 Aug 2019	Modifications of efficacy and patient reported outcomes endpoints: 
 • Only descriptive summary will be provided for primary efficacy and selected secondary endpoints. • No summary/analysis will be done for tertiary/exploratory endpoints. Appendix 8 Listing of Abbreviations was added	Study termination

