6.1.2. Percent Change from Day 29 to Day 43 in EASI

Descriptive statistics will be provided for observed percent change from Day 29 to Day 43 in EASI.

6.1.3. ISGA of Success at Days 8, 15, 22, and 29

Achievement of success in the ISGA (defined as an ISGA score of clear (0) or almost clear (1) with at least a 2-grade improvement from baseline) at Days 8, 15, 22, and 29 will be summarized. Missing data will be classified as non-responder.

6.1.4. ISGA of Clear or Almost Clear at Days 8, 15, 22, and 29

Achievement of ISGA of clear (0) or almost clear (1) at Days 8, 15, 22, and 29 will be summarized. Missing data will be classified as non-responder.

6.1.5. EASI75 at Days 8, 15, 22, and 29

Achievement of EASI75 at Days 8, 15, 22, and 29 will be summarized. Missing data will be classified as non-responder. Graph depicting proportions will be provided.

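### SAP Appendix 1 leaves the Day 43 row open-ended, so a sub-study Day 60 EASI or an unscheduled EASI can be reported as Day 43 (minor)

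*SAP*

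**What the plan says.** **Reporting windows (SAP Appendix 1).** The scope is broad: "Visit windows will be used for efficacy variables". The Day 29 row is "Days 26 to last dose +7". The Day 43 row, with target day 43, is "Last dose +8 to end of study". There is no Day 60 row and no rule on unscheduled or sub-study readings. Where readings compete, the rule is "If two or more visits fall into the same window, keep the one closest to the Target Day", and the later one is kept in a tie.

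**Where the label is used (SAP 6.1.2).** "Descriptive statistics will be provided for observed percent change from Day 29 to Day 43 in EASI". The other EASI summaries by visit stop at Day 29.

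**When EASI is taken after treatment (Protocol).**
- At the off-treatment visit, Day 43 ± 5, or 14 ± 5 days after last dose for early terminators (6.2, 6.4.4).
- At an unscheduled visit for worsening, to decide whether other treatment is allowed (6.4.5).
- In OCT sub-study subjects only: "An EASI assessment will be performed on Day 60 in addition to the Days specified in the main protocol" (Appendix 4, section 6). For everyone else Day 60 is a telephone contact (6.4.6).

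SAP 2.2 sends the sub-study analysis to a separate SAP. It does not say that the Day 60 EASI is kept out of the main analysis data.

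**The concern.** A reader will take the Day 29 to Day 43 summary as the course of EASI over the two weeks after stopping treatment. The row as written can hold two other kinds of reading.

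One is the sub-study Day 60 EASI, about a month off drug. Protocol Appendix 4 asks sites to spare the target skin sites until Day 60 but accepts that other lesions may need treatment, so this whole-body score may reflect other therapy.

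The other is an unscheduled EASI, which exists because the subject got worse and is therefore selected for a poor value.

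The table reports observed values by group, with no model between the label and the result, so what is tabulated depends entirely on the window rule.

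**Working it through.** The plan gives no figure to reproduce here. The check applies the Appendix 1 windows and tie rule to the visit days that the protocol allows. L is the day of last dose.

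**Inputs.** The end-of-treatment visit is Day 29 ± 3, with dosing to the evening before (Protocol 5.5), so L runs from 25 to 31 for completers. The scheduled Day 43 visit falls on Day 38-48. The Day 60 visit falls on Day 57-63.

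**1. Row limits.** The Day 43 row opens at L + 8:

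| L | Day 29 row | Day 43 row |
|---|---|---|
| 25 | 26-32 | 33 to end of study |
| 28 | 26-35 | 36 to end of study |
| 31 | 26-38 | 39 to end of study |

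**2. Day 60 reading only.** Every reading on Day 57-63 lies in the row, 57 - 43 = 14 to 63 - 43 = 20 days past target. With no competitor it is kept as Day 43. At L = 28, Day 60 is 60 - 28 = 32 days off drug.

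**3. Day 43 visit and Day 60 reading both present.** The visit is at most 5 days from target and the Day 60 reading at least 14, so the visit is kept. There is one exception. With L = 31 and the visit on Day 38, 31 + 7 = 38 puts the visit in the Day 29 row. There it loses to the end-of-treatment visit on Day 32 (38 - 29 = 9 days from target against 32 - 29 = 3). The Day 29 value is right, but the Day 38 visit is dropped and any Day 60 reading becomes Day 43.

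**4. Unscheduled readings.** A lone unscheduled EASI counts as Day 43 from Day 33, 36 or 39 (L = 25, 28, 31). It also displaces a scheduled visit that is further from target: unscheduled Day 42 (1 day away) beats a scheduled visit on Day 46 (3 days away).

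**5. Early terminators.** The target stays at Day 43 although their follow-up is timed from last dose. With L = 14, the off-treatment visit is about Day 28 (15 days from target). A sub-study visit 28 days after last dose is Day 42 (1 day from target), so the later reading is kept. This does not reach SAP 6.1.2, however: the Day 29 row would run from Day 26 to Day 21, which is empty, so there is no Day 29 value to change from. The Day 29 row is non-empty only when L + 7 ≥ 26, that is L ≥ 19.

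**6. Size.** The sub-study plans about 60 subjects (Appendix 4). SAP 5.1 says 40% of planned participants were enrolled; applied to the sub-study, 60 × 0.40 = 24. If 5-15% of these miss Day 43 but attend Day 60, the count is 24 × 0.05 = 1.2 to 24 × 0.15 = 3.6 readings. At full enrolment it would have been 60 × 0.05 = 3 to 60 × 0.15 = 9. The documents give no basis for counting unscheduled readings.

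**The case against.** The strongest reply is that little is left to go wrong. The nearest-reading rule settles almost every completer who attends Day 43. Reporting windows wider than visit windows are this SAP's convention. The sub-study has its own SAP, and group sizes are tabulated anyway. The study was terminated with no testing, and the change from Day 29 to Day 43 is not among the listed primary or secondary endpoints. Most of this stands, and it limits the size of the point. It does not supply a rule for subjects without a Day 43 reading or for unscheduled readings. Nor does a tabulated N distinguish scheduled from substituted values.

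A reader might infer four stronger things that the documents do not support:

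- **Uneven substitution across arms**, because half the sub-study is on hydrocortisone butyrate. That is only the 1:1:2 ratio. The planned sub-study share is 30/150 = 20% for hydrocortisone butyrate and 15/75 = 20% for Cohort 1 crisaborole. It is 15/150 = 10% for each of combined crisaborole and combined vehicle. Within each planned contrast the potential share is equal, and nothing shows that one arm misses Day 43 more often.
- **Day 60 readings taken after medication limits have ended.** Protocol 5.8.4 lifts the limits after Day 43 but excepts sub-study subjects, the only ones with a Day 60 EASI. What remains is the narrower point that their non-target lesions may be treated.
- **Subjects enrolled before Amendment 3 entering the row only when they flare.** The SAP version history lists "addition of a clinic visit at Day 43" under Amendment 3, and Protocol Section 4 says earlier subjects "should complete the version of the study for which they consented". Earlier protocol versions are not available, though. The same history entry lists the follow-up medication restrictions as new, and the unscheduled EASI serves to apply them. Earlier subjects may simply have no post-treatment EASI, which is missing data and not mislabelling.
- **Most of the row lying outside the visit window.** At L = 28 the row spans Day 36-63, 28 days, against 11 in the protocol window. That counts calendar days, not readings. By the same count the Day 8 row (Days 2-11, against 8 ± 1) is 7/10 = 70% outside.

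**Conclusion.** The point holds as a minor defect in a stated rule. The open-ended Day 43 row can report a sub-study Day 60 EASI, or an EASI taken for worsening, as Day 43, and can drop a valid scheduled visit in favour of an unscheduled one. The likely size is about 1 to 4 Day 60 readings plus an unknown number of unscheduled ones, confined to the descriptive summary in SAP 6.1.2. The Day 29 primary endpoint does not depend on this row.

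This rests on three assumptions: that the sub-study stopped at the same 40% as the main study, that 5-15% of its subjects lack a Day 43 reading but attend Day 60, and that the Day 60 EASI is in the data to which Appendix 1 is applied.

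**What to change.** In SAP Appendix 1:

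- End the Day 43 row at the protocol visit window: Day 48, or last dose +19 for early terminators.
- Admit only the scheduled off-treatment visit. The cap removes every Day 57-63 reading from completers, but not unscheduled readings inside the window, so this needs its own sentence.
- Let that scheduled visit take precedence over the Day 29 row where the two meet (Day 38 when last dose is Day 31). A Day 38-48 row without this clause would leave the overlap unresolved.
- State that the Day 60 EASI belongs to the sub-study SAP.

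In SAP 6.1.2, show by arm the number of subjects with a scheduled Day 43 visit, so that the basis of each mean is visible.

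The cost is a few lines of wording and no new data. The downside is that a few out-of-window values leave the table; they can still be listed.
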